### 2.3.2 Safety population

The safety population will consist of the patients who have signed the informed consent form and who have received at least one dose or partial dose of alirocumab.

### 2.3.3 Other analysis population

The analysis of the SIAQ® will be performed in the patients of the safety population who followed the training injection and had at least one alirocumab self-injection.

## 2.4 STATISTICAL METHODS

All statistical analyses will be descriptive and no formal statistical test will be performed.

Analyses will be performed overall and on some sub-groups of interest such as:

- Patients included in each of the risk groups at inclusion (see [Section 1.1](#)) enrolled patients who did not fulfill inclusion criterion I 03 will not be considered for this subgroup analysis. However, they will be part of the overall analysis.
- Patients with heFH / non-familial FH.
- Type 1 and Type 2 diabetes mellitus / patients without diabetes.
- Established CHD or other CVD (including patients suffering from progressive cardiovascular disease).

Results will be reported globally without regional subgroups.

The results per country if sample size is sufficient ( $\geq 30$ ), or by pooled countries if sample size is not sufficient ( $< 30$ ), will not be displayed in this Statistical Analysis Plan but it will be displayed in post-hoc analysis if it is necessary and asked by the medical countries affiliates.

*(Since some countries will include a small number of patients, the statistical results for these countries will have to be interpreted with caution. Likewise, some sub-groups might include a very small number of patients and the statistical results will have to be discussed when analysis will be displayed in post-hoc. Suggested pooled countries could be as follows: Denmark with Finland; Germany with Belgium; Slovakia with Czech Republic; and the last one, Slovenia with Hungary, Romania, and Greece).*

Final analysis will be performed after the global Data Base Lock.

Efficacy analysis, AEs analysis and demographics description will be displayed overall, and by the sub-groups of interest described above.

#### **2.4.1 Demographics and baseline characteristics**

Parameters described in [Section 2.1.1](#) (demographic characteristics, medical history including medical history of specific interest, disease characteristics at baseline, starting dose of alirocumab, other baseline characteristics) will be summarized using descriptive statistics.

The number and percentage of patients will be provided for qualitative variables. The following information will be provided for continuous variables: number of patients, mean, standard deviation, median, as well as Min and Max, first quartile (Q1) and third quartile (Q3).

Parameters will be summarized in the safety population. The analyses will also be performed in the mITT population only if the number of patients in the mITT population is below 90% of the number of patients in the safety population.

Medical history of specific interest (see [Section 2.1.1](#)) will be presented according to the terms pre-listed in the eCRF and will be displayed overall and by groups at inclusion (A, B, C, D, E) using the number and the proportions of patients.

Other relevant medical/surgical history will be presented by primary SOC and PT. The tables will be sorted by SOC internationally agreed order and decreasing frequency of PT based on the overall incidence.

For each type of hypercholesterolemia (heFH/non-FH), the LDL-C value at entry in the study will be described quantitatively and qualitatively ( $<70$ ,  $\geq 70$  to  $<100$ ,  $\geq 100$  to  $<130$ ,  $\geq 130$  to  $<160$ ,  $\geq 160$  to  $<190$ ,  $\geq 190$  mg/dL, ie,  $<1.81$ ,  $\geq 1.81$  to  $<2.59$ ,  $\geq 2.59$  to  $<3.37$ ,  $\geq 3.37$  to  $<4.14$ ,  $\geq 4.14$  to  $<4.91$ ,  $\geq 4.91$  mmol/L, overall and by inclusion criteria, ie, by groups A, B, C, D or E. Note that any patient could contribute to several inclusion groups.

The starting dose of alirocumab at the entry of patients in the study will be described. The number and proportion of patients for whom alirocumab was started at 75 mg (respectively 150 mg) will be summarized:

- Overall.
- by classes of baseline LDL-C level (<70,  $\geq 70$  to <100,  $\geq 100$  to <130,  $\geq 130$  to <160,  $\geq 160$  to <190,  $\geq 190$  mg/dL, ie, <1.81,  $\geq 1.81$  to <2.59,  $\geq 2.59$  to <3.37,  $\geq 3.37$  to <4.14,  $\geq 4.14$  to <4.91,  $\geq 4.91$  mmol/L).
- by diagnosis of heterozygous familial hypercholesterolemia.
- by diagnosis criteria, ie, groups A, B, C, D, E at the enrollment in the study.

The LDL-C values will also be quantitatively summarized for each level of starting dose.

The person who gave the injection of alirocumab at inclusion will be described by the number and the proportion of patients in each of the following categories: patient, designated person, site staff. In addition, among patients who self-injected, the proportion of patients who performed themselves their training injection with placebo will be indicated.

#### **2.4.2 Prior or concomitant medications**

The prior and concomitant medications will be presented for the safety population.

Medications will be summarized according to the WHO-DD, considering the first digit of the anatomic category (ATC) class (anatomic category) and the first 4 digits of the ATC class (therapeutic category). All ATC codes corresponding to a medication will be summarized, and patients will be counted once in each ATC category (anatomic or therapeutic) linked to the medication. Therefore patients may be counted several times for the same medication.

The table for prior medications will be sorted by decreasing frequency of ATC followed by all other therapeutic classes based on the overall incidence.

The tables for concomitant will be sorted by decreasing frequency of ATC followed by all other therapeutic classes. In case of equal frequency regarding ATCs (anatomic or therapeutic categories), alphabetical order will be used.

The tables of prior and concomitant medications will be performed by each one of the following categories:

- Lipid modifying therapies (for these tables, the medications will be displayed taking into account the classification of “Statins” and “Other than statins” as well).
- Cardiovascular drugs.
- Other.

#### **2.4.3 Extent of investigational medicinal product exposure and compliance**

The extent of study treatment exposure and compliance will be assessed and summarized within the safety population ([Section 2.3.2](#)).

#### **2.4.3.1 Extent of investigational medicinal product exposure**

The total exposure will be assessed using descriptive statistics for:

- Duration of alirocumab exposure in weeks defined as:  
(last alirocumab injection date + 14 - first alirocumab injection date)/7, regardless of unplanned intermittent discontinuations. Non-integer values will be rounded to one decimal place.
- Total number of alirocumab injections by patient.

These quantitative parameters will be summarized using number, mean, standard deviation (SD), median, Q1, Q3, Min, and Max.

In addition, duration of treatment exposure will also be summarized categorically by number and percentages for each of the following categories and cumulatively according to these categories:

- 1 day  $\leq$  duration <4 weeks
- 4 weeks  $\leq$  duration <8 weeks
- 8 weeks  $\leq$  duration <12 weeks
- 12 weeks  $\leq$  duration <18 weeks
- 18 weeks  $\leq$  duration <24 weeks
- 24 weeks  $\leq$  duration <36 weeks
- 36 weeks  $\leq$  duration <48 weeks
- 48 weeks  $\leq$  duration <60 weeks
- 60 weeks  $\leq$  duration <72 weeks
- 72 weeks  $\leq$  duration <84 weeks
- 84 weeks  $\leq$  duration <96 weeks
- 96 weeks  $\leq$  duration <108 weeks
- duration  $\geq$ 108 weeks

The number of patients who gave themselves a training injection (with placebo) will also be described.

#### **2.4.3.2 Compliance**

Compliance will be assessed using the following parameters:

- The mean injection frequency of alirocumab will be defined for each patient as the average number of days between 2 consecutive injections, that is:  
(last dose date - first dose date)/(number of injections -1) for patients receiving at least 2 injections.
- The overall compliance will be defined for each patient as:  
(number of injections performed during the study period/number of theoretical injections to be performed during the study period)\*100. The number of theoretical injections will be defined for each patient as: (last injection date - first injection date)/14.

- Number and percentage of patients who discontinued temporarily, with delayed injections and/or partially administered injections will be described. For patients with temporary discontinuations, the number of injections not performed will be displayed.

These parameters will be summarized descriptively (N, Mean, SD, Median, minimum [Min] and maximum [Max]).

The percentage of patients whose overall compliance for injections is <80% will be also summarized.

According to protocol, cases of overdose are reported in the AE eCRF pages and will be described in the AE analysis (see [Section 2.4.5.1](#)).

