##### ***11.4.1.2 Compliance***

Compliance will be assessed using the following parameters:

- The mean injection frequency will be defined for each patient as the average number of days between 2 consecutive injections, that is: (last dose date – first dose date)/(number of injections -1).

This parameter will be summarized descriptively (N, Mean, SD, Median, Min and Max).

- The overall compliance will be defined for each patient as: 100 - (% days with under-planned dosing + % days with above-planned dosing). Under-planned and above-planned dosing will be defined as follows, considering that injections should be performed every 2 weeks (  $\pm 3$  days):
  - The % days with under-planned dosing will be defined for each patient as the number of days with no injection administered within the previous 17 days divided by the duration of IMP injection exposure in days. For example, if a patient takes a dose 18 days after his/her previous injection, then 1 day is counted as a day under-planned dosing,
  - The % days with above-planned dosing will be defined for each patient as the number of days with more than one injection administered within the 11 days before divided by the duration of IMP injection exposure in days. For example, if a patient takes a dose 9 days after his/her previous injection, then 2 days are counted as a days above-planned dosing.

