### **2.2.1 Enrollment and drug dispensing irregularities**

This is an open-label study and every patient will receive alirocumab. Treatment kit numbers will be allocated via interactive voice/web response system (IVRS/IWRS).

Each alirocumab treatment kit will be prepared to contain 6 pre-filled pens.

In addition to the alirocumab treatment kits, a training kit containing 1 placebo pre-filled pen will be prepared for the purpose of instructing patients on injection administration. The content of the labelling is in accordance with the local regulatory specifications and requirements.

Enrollment and drug-dispensing irregularities will be monitored throughout the study and reviewed on an ongoing basis. They will be documented in the clinical study report. The irregularities will be categorized and summarized among enrolled patients (number and percentages).

Enrollment and drug-dispensing irregularities to be prospectively identified include but are not limited to:

- Kit dispensation without IVRS transaction.
- Erroneous kit dispensation.
- Kit not available.
- Enrolled by error.
- Patient enrolled twice.

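### The SAP compliance formula divides injections by intervals, so perfect adherence exceeds 100%, one injection gives 1/0, and the <80% count misses poor compliers

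*SAP*

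**What the plan says.** SAP 2.4.3.2 gives overall compliance as injections performed divided by theoretical injections, times 100. On the denominator it states: "The number of theoretical injections will be defined for each patient as: (last injection date - first injection date)/14". It also plans a low-compliance output: "The percentage of patients whose overall compliance for injections is <80% will be also summarized".

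Three nearby SAP rules bear on the same count:

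- The mean injection interval, in the bullet just above, is "last dose date - first dose date)/(number of injections -1) for patients receiving at least 2 injections". It divides by one fewer than the injections and excludes single-injection patients.
- Exposure in weeks (SAP 2.4.3.1) is "last alirocumab injection date + 14 - first alirocumab injection date)/7". It adds the two weeks covered by the last injection.
- On supply, SAP 2.2.1 states: "Each alirocumab treatment kit will be prepared to contain 6 pre-filled pens".

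Compliance is summarised in the safety population (SAP 2.4.3), which a patient enters with one full or partial dose (SAP 2.3.2).

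Protocol 11.4.1.2 defines overall compliance differently, as "100 - (% days with under-planned dosing + % days with above-planned dosing"), where under-planned dosing is the "number of days with no injection administered within the previous 17 days" divided by days of exposure.

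**The concern.** The ratio mixes two kinds of count. Between the first and last injection, both included, a two-weekly schedule has one more injection than it has 14-day intervals. The numerator uses injections and the denominator uses intervals.

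Three things follow. Compliance is overstated, relative to the injections due, for every patient with at least two injections. It is undefined for a patient with one. The 80% cut-off becomes too lenient, so the pre-specified count of poor compliers is too low.

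The overstatement also depends on exposure. It is largest for short treatment, and duration in this study varies by country from 12 weeks upwards, so shorter treatment will look like better compliance. The protocol's definition subtracts two non-negative percentages from 100 and cannot exceed 100%. The SAP formula that replaces it can.

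**Working it through.** **Inputs.** Interval 14 days (two-weekly dosing, SAP 1.1); threshold strictly below 80% (SAP 2.4.3.2); exposure formula from SAP 2.4.3.1. The documents state no compliance value to reproduce. The protocol's two worked examples do reproduce: an 18-day gap gives 18 - 17 = 1 under-planned day, and a 9-day gap gives 11 - 9 = 2 above-planned days.

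**Internal check at 12 weeks.** With the last injection 70 days after the first:

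- Exposure = (70 + 14)/7 = 12.0 weeks, which is 6 two-week dosing periods, or one 6-pen kit.
- SAP theoretical injections = 70/14 = 5.

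**Perfect adherence.** With exact 14-day spacing, the SAP score is n/(n-1):

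| Injections | SAP score |
|---|---|
| 1 | 1/0, undefined |
| 2 | 2/1 = 200% |
| 6 | 6/5 = 120% |
| 7 | 7/6 = 116.7% |
| 13 | 13/12 = 108.3% |
| 25 | 25/24 = 104.2% |
| 61 | 61/60 = 101.7% |

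**The <80% count.** For N scheduled injections with k taken, including the first and last, the SAP score is k/(N-1) and the correct score is k/N. The table gives the largest k flagged as below 80%.

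| N | SAP | Correct | Patient missed |
|---|---|---|---|
| 6 | 3 | 4 | 4/6 = 66.7%, scored 4/5 = 80.0% |
| 7 | 4 | 5 | 5/7 = 71.4%, scored 5/6 = 83.3% |
| 13 | 9 | 10 | 10/13 = 76.9%, scored 10/12 = 83.3% |
| 25 | 19 | 19 | none |
| 26 | 19 | 20 | 20/26 = 76.9%, scored 20/25 = 80.0% |
| 60 | 47 | 47 | none |
| 61 | 47 | 48 | 48/61 = 78.7%, scored 48/60 = 80.0% |

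Enumerating N = 2 to 66, the cut-off moves by exactly one injection except when N is a multiple of 5, where it does not move.

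**Protocol definition for the two short-exposure patients.** Two interior injections are missed and the rest are on time. Two separate 28-day gaps give 2 x (28 - 17) = 22 under-planned days; one 42-day gap gives 42 - 17 = 25.

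- 4 of 6, exposure 70 + 14 = 84 days: 100 - 100 x 22/84 = 73.8%, or 100 - 100 x 25/84 = 70.2%.
- 5 of 7, exposure 84 + 14 = 98 days: 100 - 100 x 22/98 = 77.6%, or 100 - 100 x 25/98 = 74.5%.

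Both patients are below 80% on the protocol's own definition.

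**Sensitivity to the last injection date.**

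- 4 of 6: 4 x 14/70 = 80.0% at 70 days, but 4 x 14/71 = 78.9% at 71 days. The patient escapes at 67 to 70 days and is counted at 71 to 73.
- 5 of 7: 5 x 14/87 = 80.5% at 87 days and 5 x 14/88 = 79.5% at 88 days. The patient escapes throughout 84 ± 3 days.

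**The case against.** The strongest case on the other side accepts the counting error and disputes its weight.

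- **Knife-edge example.** The 4-of-6 patient sits exactly on the threshold, and a last injection one day late removes the case. This stands for that example, which escapes at 4 of the 7 last-injection dates within ± 3 days. It does not stand for 5 of 7, which escapes at all of them.
- **The protocol does not always agree with the corrected count.** At longer exposure it can score the missed patients above 80%. For 10 of 13 (182 days), three separate misses give 100 - 100 x 33/182 = 81.9%. For 48 of 61 (854 days), thirteen separate misses give 100 - 100 x 143/854 = 83.3%. This stands, so the protocol supports the misclassification here only near 12 weeks.
- **Overstatement needs a reference.** Six injections 17 days apart score 6 x 14/85 = 98.8% on the SAP formula and 100% on the protocol's. This stands: the overstatement is relative to the number of injections due.
- **The effect fades.** With 60 scheduled injections (120 weeks of exposure) the cut-off does not move. This also stands.
- **Other outputs reveal the problem.** A maximum above 100% would be visible, and the mean interval would be 70/3 = 23.3 days for 4 of 6 and 84/4 = 21 days for 5 of 7. These outputs expose the error but do not correct the <80% count. Injections not performed are displayed only for temporary discontinuations.
- **Nothing inferential depends on it.** SAP 2.4 states: "All statistical analyses will be descriptive and no formal statistical test will be performed". There is no comparator arm. This limits the importance of the point, but the reported number would still be wrong.

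**Conclusion.** The concern holds. Followed as written, SAP 2.4.3.2 inflates overall compliance, gives no value for single-injection patients, and undercounts those below 80%. For exact two-weekly dosing the inflation is 20 percentage points at 6 injections and 1.7 at 61. The clearest misclassification is near the 12-week minimum, where patients at 66.7% and 71.4% can escape the count. At longer exposure the missed patients are close to 80%.

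These figures assume that injections otherwise fall on 14-day multiples and that the first and last scheduled injections are both taken. The consequence is limited to a descriptive summary, but a pre-specified output is wrong, so it should be fixed. A secondary point is traceability: SAP 1.5 does not list the replacement of the protocol's compliance definition, and SAP 1.6 reports no modifications.

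**What to change.** Define theoretical injections as (last injection date - first injection date)/14 + 1. Exact two-weekly dosing then scores 100% at every n, and the two short-exposure patients score 66.7% and 71.4%, both counted as below 80%. State how single-injection patients are handled, for example by restricting the measure to at least two injections, as the adjacent mean-interval bullet does. The alternative is to restore the day-based definition in Protocol 11.4.1.2. If the SAP keeps an injection-count measure, record the departure from the protocol in SAP 1.5 or 1.6.

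The cost is one term and one sentence, with no new data. Reported compliance becomes slightly less favourable.

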  - An overdose (accidental or intentional) is an event suspected by the Investigator or spontaneously notified by the patient (not based on systematic injection counts) and defined as at least twice of the intended dose within the intended therapeutic interval (ie, 2 or more injections of the study treatment are administered in  $<7$  calendar days). The symptomatic overdose should be reported using the term "symptomatic overdose (accidental or intentional)", indicating the circumstance in parentheses (eg, "symptomatic overdose [accidental]" or "symptomatic overdose [intentional]"). The patient should be monitored and appropriate symptomatic treatment instituted,
  - The circumstances of the overdose should be clearly specified in the verbatim, and the symptoms, if any, entered on separate AE/SAE forms,
  - Of note, asymptomatic overdose should be reported as a standard AE.

- **Neurologic events:**
  - Neurologic events that require additional examinations/procedures and/or referral to a specialist should be reported as an AESI. If the event does not require additional examinations/procedures and/or referral to a specialist, it should be reported as a standard adverse event.
- **Neurocognitive events:**
  - All neurocognitive events will be considered as AESI.

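### The SAP replaces the protocol's date-based dosing measure with a count ratio, without listing the change, so above-planned dosing is never counted and extra injections offset by missed ones cannot be seen

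*SAP*

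**What the plan says.** Protocol 11.4.1.2 defines two date-based quantities around a 14-day interval with 3 days' tolerance. Under-planned dosing is the "number of days with no injection administered within the previous 17 days divided by the duration of IMP injection exposure in days". Above-planned dosing is the "number of days with more than one injection administered within the 11 days before divided by the duration of IMP injection exposure in days". Overall compliance is 100 minus the sum of the two percentages.

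SAP 2.4.3.2 keeps the mean injection interval but drops both percentages. Overall compliance becomes injections performed divided by theoretical injections, times 100, where the theoretical number is (last date − first date)/14. The section summarises these parameters by N, mean, SD, median, minimum and maximum. It also reports patients with temporary discontinuation, delayed or partial injections, and the percentage of patients below 80%. It has no item for early or extra injections and no upper threshold. For overdose it states: "According to protocol, cases of overdose are reported in the AE eCRF pages and will be described in the AE analysis".

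Protocol 10.4.1.3 defines overdose as suspected by the investigator or notified by the patient, "not based on systematic injection counts", and as two or more injections in fewer than 7 calendar days. SAP 2.1.4.1 selects symptomatic cases by the site's AESI category and adds two wider analyses of reported events using the MedDRA term for overdose.

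SAP 1.5 lists changes as small as a slightly altered mITT definition and an added condition for the SIAQ population. It does not mention compliance. SAP 1.6 is marked not applicable.

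**The concern.** The protocol's two components add, so irregularity in either direction lowers compliance. In a ratio of counts, an early or extra injection makes up for a missed one. A patient who alternates between long and short intervals can then look identical to one who injects every 14 days. The early side of that pattern has no other place in the outputs, because the SAP tabulates only the late side.

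Documenting safety is part of the primary objective, and after the inclusion visit injections take place outside the clinic (Protocol 8.1.2). A reader of the report would expect to learn how often dosing was closer together than planned. The protocol planned to say so; the SAP does not, and does not record that it stopped.

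**Working it through.** **Inputs.** Limits of 17 and 11 days come from Protocol 11.4.1.2. Exposure in days is last − first + 14 (Protocol 11.4.1.1, before division by 7). The SAP ratio and the mean interval come from SAP 2.4.3.2.

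**Formulas.** For each interval g between consecutive injections:

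- under-planned days = max(0, g − 17); above-planned days = max(0, 11 − g)
- protocol compliance = 100 − 100 × (under + above)/(last − first + 14)
- SAP ratio = 100 × n/((last − first)/14)
- mean interval = (last − first)/(n − 1)

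**Reproducing the protocol's figures.** The protocol says "if a patient takes a dose 18 days after his/her previous injection, then 1 day is counted as a day under-planned dosing": 18 − 17 = 1. It also says "if a patient takes a dose 9 days after his/her previous injection, then 2 days are counted as a days above-planned dosing": 11 − 9 = 2. Both match.

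**Cancellation over 12 weeks.** Each illustrative patient has 7 injections, a first-to-last span of 84 days and exposure of 98 days. The SAP ratio is 7/(84/14) = 7/6 = 116.7% and the mean interval is 84/6 = 14.00 days for every row.

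| Intervals (days) | Under-planned days | Above-planned days | Protocol compliance |
|---|---|---|---|
| 14 × 6 | 0 | 0 | 100.0% |
| 14, 28, 14, 7, 7, 14 | 11 | 8 | 80.6% |
| 7, 7, 28, 14, 7, 21 | 15 | 12 | 72.4% |
| 8, 20 repeated three times | 9 | 9 | 81.6% |
| 3, 25 repeated three times | 24 | 24 | 51.0% |

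For the third row: under = (28 − 17) + (21 − 17) = 15; above = 3 × (11 − 7) = 12; 100 − 100 × 27/98 = 72.4%.

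That a perfect patient scores 116.7% is a separate defect: the denominator does not count the first injection. Adding one gives 7/7 = 100% in every row, so the cancellation remains.

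**Longer exposure.** Over 120 weeks (840 days, 61 injections), a perfect patient scores 61/60 = 101.7% in the SAP. A patient with three missed and three extra injections also scores 101.7%, but has 33 under-planned and 24 above-planned days: 100 − 100 × 57/854 = 93.3% under the protocol.

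**What still shows.** Excess that is not offset moves both SAP measures. Weekly dosing for 12 weeks gives a mean interval of 84/12 = 7.00 days and a ratio of 13/6 = 216.7%. One extra injection in 12 weeks gives 84/7 = 12.00 days and 8/6 = 133.3%.

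**Effect of late injections.** Under Protocol 8.1.2, an injection up to 7 days late is given and the original schedule resumed. A delay of d days gives intervals of 14 + d and 14 − d. For d from 4 to 7, each delay adds d − 3 under-planned and d − 3 above-planned days. One 7-day delay (21, 7, then 14 × 4) gives 4 + 4 = 8 days and 91.8%. Three such delays (21, 7 repeated) give 12 + 12 = 24 days and 75.5%, with all seven injections given.

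**The case against.** A reader might infer that too-frequent dosing goes unreported. That is too strong. SAP 2.4.3.1 summarises total injections, and SAP 2.4.3.2 gives the minimum of the mean interval and the maximum of compliance, so sustained net excess leaves a trace. The trace is limited: extremes describe single patients, total injections vary with time on treatment, and a value above 100% arises with perfect dosing.

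A reader might also infer that only patients below 80% are reported. They are not the only ones. Cancellation needs a long gap, and delayed injections and temporary discontinuations are tabulated. What is lost is the early side.

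Nor do the AE pages exclude injection counts. It is the overdose definition that is not built on them. Diaries and kits are reviewed at visits, so an investigator could suspect overdose from the dates, and the SAP's overdose analyses follow the protocol. The compliance formula does not alter capture of symptomatic overdose.

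The strongest objection is that intervals of 7 to 10 days can arise from the late-injection instruction in Protocol 8.1.2 with no extra drug given, and that the protocol's formula counts each such delay on both sides. The 75.5% case shows this. A count ratio is therefore a defensible descriptive choice, and Protocol 11 allows the plan to be revised. This stands against making the protocol's overall figure the sole basis for the 80% count. It does not answer the loss of the separate above-planned figure or the missing entry in SAP 1.5.

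**Conclusion.** The point holds in a limited form. The SAP drops a prespecified date-based measure without listing the change. Its two remaining measures cannot show extra injections offset by missed ones, and no output gives the number of patients, days or intervals with above-planned dosing. AE-reported overdose is not a substitute, because it depends on suspicion or notification and stops at intervals under 7 days.

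In the constructed 12-week patients, the same SAP result (116.7%, mean interval 14.00 days) corresponds to protocol compliance anywhere from 51.0% to 100.0%. These are illustrations, not trial data, and the documents give no basis for estimating how many patients are affected. The documents do not support reading every short interval as excess drug or as a missed overdose. The conclusion assumes that individual injection dates are available for analysis; Protocol 10.2 lists administration dates as source data, and SAP 2.5.1 refers to an injection administration case report form page.

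**What to change.** In SAP 2.4.3.2:

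- Restore the protocol's percentage of days under-planned and percentage of days above-planned as separate summaries.
- Show the protocol's overall compliance beside the count ratio, and give the below-80% count for both.
- Add the number and percentage of patients with any inter-injection interval under 7 days and with any under 11 days, from the recorded dates, placed beside the AE-reported overdoses.
- Identify short intervals that directly follow a delayed injection handled under Protocol 8.1.2, so that they are not read as extra drug.

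In SAP 1.5, list the change of compliance measure and the reason for it.

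This changes no dosing instruction and needs no new data, given the recorded dates. The cost is one more derivation and table, and reported compliance that is slightly less favourable.
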